9.4.2. Treatment Period

After randomization, the 12-Week Treatment Period of the study will begin (Table 7). A study visit window of \pm 3 days is permitted at each visit beginning with Week 2/Day 15 (PFT and OCT assessments have a window of \pm 7 days). For the Week 12 through Week 48 Visits, and ET Visit, a study visit window of \pm 7 days is permitted. For the Week 52 Visit, a study visit window of \pm 14 days is permitted. Study visits should be scheduled for the morning.

The subscores for SF and RB are derived from the subject eDiary entries. On visits when MMS is calculated, these subscores are derived using the scores from the 3 most recent consecutive days within the 7 days prior to the day of bowel preparation (excluding the day of bowel preparation), averaged and rounded to the nearest integer. If 3 consecutive days are not available, then the average of the 2 most recent consecutive days within the 7 days will be used.

On visits without endoscopy, the SF and RB subscores are derived using the scores from the 3 most recent consecutive days within the 7 days prior to the date of visit, averaged and rounded

to the nearest integer. If 3 consecutive days are not available, then the average of the 2 most recent consecutive days within the 7 days will be used.

It is recommended that procedures are performed in a consistent order and at approximately the same time of day for each visit. Below is the recommended sequence of events:

- Questionnaire administration
- Adverse event review
- Vital signs
- 12-lead ECG (as indicated in the Schedules of Assessments, [Table 7](#) and [Table 8](#))
- Physical examination
- EIMs (as indicated in the Schedules of Assessments, [Table 7](#) and [Table 8](#))
- PFT (as indicated in the Schedules of Assessments, [Table 7](#) and [Table 8](#))
- OCT (as indicated in the Schedules of Assessments, [Table 7](#) and [Table 8](#))
- Blood sample collection for laboratory tests and pre-dose PK sampling

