16. APPENDICES

APPENDIX 1: SCHEDULES OF ASSESSMENTS

Table 7: Schedule of Assessments – Screening and 12-Week Treatment Period

| Evaluation | Screening Period | 12-Week Treatment Period | | | | | 2-Week Follow-Up Visit ^b ± 3 Days | 4-Week Follow-Up Visit ^b ± 3 Days |
|---------------------------------------------------------------------|------------------|--------------------------|--------------------|--------------------|--------------------|------------------------------------------------------|-------------------------------------------------|-------------------------------------------------|
| | -28 to -1 | W0/D1 | W2/D15 ± 3 Days | W4/D29 ± 3 Days | W8/D57 ± 3 Days | W12/D85 / Early Termination ^a ± 3 Days | | |
| Informed consent | X | | | | | | | |
| Inclusion/exclusion criteria | X | X | | | | | | |
| Demographics | X | | | | | | | |
| Medical and social history ^c | X | | | | | | | |
| Ulcerative colitis history | X | | | | | | | |
| Chest X-ray ^d | X | | | | | | | |
| Tuberculosis test ^e | X | | | | | | | |
| Tuberculosis questionnaire ^e | X | X | X | X | X | X | X | X |
| Virology screen (HIV, HBV, HCV) ^f | X | | | | | | | |
| Randomization | | X | | | | | | |
| eDiary instruction ^g | X | | | | | | | |
| eDiary review | | X | X | X | X | X | | |
| MMS ^h | | X | | | | X | | |
| Stool frequency and rectal bleeding subscore ⁱ | | X | X | X | X | X | | |
| PGA for total Mayo Clinic Score | | X | | | | X | | |
| IBDQ, UC-PRO/SS, SF-36, WPAI-UC, and abdominal pain and urgency NRS | | X | | | | X | | |
| Adverse event assessment | X | X | X | X | X | X | X | X |
| Vital signs ^j | X ^j | X ^{i,k} | X | X | X | X | X | X |

| Evaluation | Screening Period | 12-Week Treatment Period | | | | | 2-Week Follow-Up Visit ^b ± 3 Days | 4-Week Follow-Up Visit ^b ± 3 Days |
|------------------------------------------------------------------|------------------|--------------------------|--------------------|--------------------|--------------------|------------------------------------------------------|-------------------------------------------------|-------------------------------------------------|
| | -28 to -1 | W0/D1 | W2/D15 ± 3 Days | W4/D29 ± 3 Days | W8/D57 ± 3 Days | W12/D85 / Early Termination ^a ± 3 Days | | |
| 12-lead ECG ^l | X ^l | X ^{l,m} | | | | X | | |
| Physical examination ⁿ | X | X | X | X | X | X | X | X |
| Extraintestinal manifestations ^o | X | | | | | X | X | X |
| Pulmonary function test ^p | X ^q | | | | | X ^q | X ^q | |

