| Ophthalmoscopy with OCT | X ^r | | | | | X ^r | X ^r | |
| Urine drug screen ^s | X | | | | | | | |
| Pregnancy test ^t | X | X | | X | X | X | | X |
| Genomic DNA (optional) | | X | | | | | | |
| CBC with differential and platelets | X | X | X | X | X | X | X | X |
| TBNK | X | X | X | X | X | X | X | X |
| Laboratory tests including hs-CRP ^u | X | X | X | X | X | X | X | |
| Stool sample/fecal calprotectin ^v | X | | X | X | X | X | | |
| Stool sample for microbiome | X | | | | | X | | |
| Flexible proctosigmoidoscopy/colonoscopy and biopsy ^w | X | | | | | X | | |
| PK assessments ^x | | X | X | X | X | X | X ^x | X ^x |
| Biomarkers blood sample ^y | | X | | | | X | | |
| Concomitant medications and procedures ^z | | X | X | X | X | X | X | X |
| Drug dispensation/ accountability | | X | X | X | X | X ^{aa} | | |
| Study treatment administration ^{bb} | | X – Once daily | | | | | | |

- ^a All visits beyond W0/D1 may be virtual/hybrid visits (Section 9.6). Subjects discontinuing prior to Week 12/Day 85 should have an Early Termination (ET) visit within 7 days of the last study treatment administration and before initiation of any new treatments. For subjects who complete Week 12, the Week 12 visit will be used to begin assessing eligibility for the APD334-303 OLE study.
- ^b For subjects not participating in the APD334-303 OLE study, a follow-up visit will be performed at 2 and 4 weeks after the last administration of study treatment. If the ET or Study Completion visit is ≥ 2 weeks after the last dose of study treatment, the 2-Week Follow-Up visit is not required; however, the 4-Week Follow-Up visit should be scheduled and completed. If the ET or Study Completion visit is ≥ 4 weeks after the last administration of study treatment, the 4-Week Follow-Up visit is not required. If the absolute peripheral lymphocyte count is not within normal limits at the 4-Week Follow-Up visit, subjects should return for CBC with differential according to local standard of care (captured as subsequent Follow-Up visit or unscheduled visit).
- ^c Medical history, including prior and ongoing medication use, will be collected during screening and should be updated for any new conditions or medications as needed prior to dosing at the D1 visit (Section 9.3.5).
- ^d A chest X-ray taken within the previous 6 months from the Screening Visit may also be used.

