^{bb} On days with scheduled study visits, subjects should not take their dose of study treatment at home in order to complete pre-dose study procedures. The dose will be taken at the study site after blood draws for PK and after all pre-dose assessments and procedures have been completed.

AV, atrioventricular; β -hCG, beta-human chorionic gonadotropin; BP, blood pressure; CBC, complete blood count; D, day; DLCO, diffusing capacity of the lungs for carbon monoxide; ECG, electrocardiogram; eDiary, electronic diary; EIM, extraintestinal manifestations; FEV₁, forced expiratory volume at 1 second; FVC, forced vital capacity; hepatitis B surface antigen; HBV, hepatitis B virus; HCV, hepatitis C virus; HIV, human immunodeficiency virus; HR, heart rate; hs-CRP, high-sensitivity C-reactive protein; IBDQ, Inflammatory Bowel Disease Questionnaire; MDR, multi-drug resistant; MMS, modified Mayo score; NRS, numeric rating scale; OCT, optical coherence tomography; OLE, open-label extension; PGA, Physicians Global Assessment; PK, pharmacokinetics; QTcF, Fridericia's corrected QT interval; RB, rectal bleeding; SF, stool frequency; SF-36, Medical Outcomes Study 36-Item Short Form Health Survey; TBNK, T lymphocytes, B lymphocytes, and Natural Killer lymphocytes; TB, tuberculosis; UC, ulcerative colitis; UC-PRO/SS, Ulcerative Colitis Patient-Reported Outcomes Signs and Symptoms; W, week; WHO, World Health Organization; WPAI UC, Work Productivity and Activity Impairment Questionnaire – Ulcerative Colitis

Table 8: Schedule of Assessments – 40-Week Treatment Period

| Evaluation | 40-Week Treatment Period | | | | | | | 2-Week Follow-Up Visit ^b ± 3 Days | 4-Week Follow-Up Visit ^b ± 3 Days |
|-----------------------------------------------------------|--------------------------|--------------------------|--------------------------|--------------------------|--------------------------|--------------------------|-----------------------------------------------------------------------|-------------------------------------------------|-------------------------------------------------|
| | W16/ D113 ± 7 Days | W20/ D141 ± 7 Days | W24/ D169 ± 7 Days | W32/ D225 ± 7 Days | W40/ D281 ± 7 Days | W48/ D337 ± 7 Days | W52/D365 ± 14 Days / Early Termination ^a ± 7 Days | | |
| eDiary review | X | X | X | X | X | X | X | | |
| MMS ^c | | | | | | | X | | |
| Stool frequency and rectal bleeding subscore ^d | X | X | X | X | X | X | X | | |

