| Appendix 1: Schedules of Assessments, Table 8: Schedule of Assessments | Revised column header as follows: “W52/D365 ± 14 Days/Early Termination ^a ± 7 Days” | To enable critical visit assessments to be made in the event that facilities are inaccessible due to various logistic or operational constraints |
| Appendix 1: Schedules of Assessments Table 7: Schedule of Assessments, Footnote y Table 8: Schedule of Assessments, Footnote o | Added “Biomarker sample collection is not required at Early Termination visit.” | Footnote added to clarify sample collection needed at Early Termination |
| Appendix 1: Schedules of Assessments, Table 7: Schedule of Assessments, Footnote r Table 8: Schedule of Assessments, Footnote h and Footnote i | Revised second sentence in the footnote to: “The 2-Week Follow-Up visit assessment is only required if clinically indicated.” | To reduce patient burden, the necessity of conducting OCTs during follow up is only required if clinically indicated |

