6.4. Windowing Conventions

All scheduled study visits are defined relative to Study Day 1, the date of first dose. Scheduled visit windows are defined in Clinical Study Protocol APD334-301 Appendix 1. A windowing convention will be used to determine the analysis visit value for a given measurement and will be applicable for all by-visit summaries and analyses for efficacy and safety data. Refer to [Table 2](#) for specific visit windows.

Table 2: Visit Windows for Efficacy and Safety Analyses

For all efficacy (except endoscopy/MMS/histology), efficacy-related biomarkers, safety labs and vital signs	
Scheduled Study Visit (Protocol Scheduled Day)	Analysis Visit Window (Study Day)
Baseline	≤ 1
Week 0 (Day 1)	1
Week 0 (Day 2) ^a	2
Week 2 (Day 15 ± 3)	2 to 22, or 3 to 22 ^a
Week 4 (Day 29 ± 3)	23 to 43
Week 8 (Day 57 ± 3)	44 to 71
Week 12 (Day 85 ± 7)	72 to 99
Week 16 (Day 113 ± 7)	100 to 127
Week 20 (Day 141 ± 7)	128 to 155
Week 24 (Day 169 ± 7)	156 to 197
Week 32 (Day 225 ± 7)	198 to 253
Week 40 (Day 281 ± 7)	254 to 309
Week 48 (Day 337 ± 7)	310 to 351
Week 52 (Day 365 ± 14)	> 351
For endoscopy/MMS/histology/all composite endpoints that include an endoscopy component and/or RB/SF component, Physician’s Global Assessment, health-related quality of life, ECGs, OCT, and PFT	
Scheduled Study Visit (Protocol Scheduled Day)	Analysis Visit Window (Study Day)
Baseline	≤ 1
Week 0 (Day 1)	1
Week 0 (Day 2) ^a	2
Week 12 (Day 85 ± 7) ^{b,c}	66 to 113 (66 to 141 for assessments impacted by COVID-19 pandemic) ^d
Week 32 (Day 225 ± 7) [PFT only]	198 to 253 (198 to 281 for assessments impacted by COVID-19 pandemic) ^d
Week 52 (Day 365 ± 14) ^{b,d}	337 to 393 (337 to 421 for assessments impacted by COVID-19 pandemic) ^e

^a Applicable only for subjects who require extended monitoring on Day 2 for vital signs and ECGs.

^b Applicable to all Week 12 and Week 52 efficacy endpoints based on any component of Mayo clinic score, such as clinical remission and symptomatic remission. Protocol visit window for PFT and OCT at Week 12 is Day 85 ± 7 (FDA 2020).

^c Due to overlapping windows at Week 12 and Week 8/16, a hierarchical algorithm will be used for the mapping. Week 12 will always be mapped first, then assess records for the Week 8/16 mapping. If a scheduled Week 8 and 12, or Week 12 and 16 visits are both present in the same visit window, they will be mapped to separate visits (ie, Week 8 and Week 12 or Week 12 and Week 16).

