If one or more results for a variable are assigned to the same analysis visit, the result with the date closest to the protocol scheduled day will be used in the analysis, except for component subscores of MMS or TMS, in which case, the composite score and component subscores from the same date will be used in the analysis. If 2 measurements in the same analysis visit window are equidistant from the protocol scheduled study day, the earliest measurement will be used in the analysis. If multiple assessments are available on the same day, then the average of the assessment will be used in the analysis, except for laboratory and ECG data where the assessment at the earliest time of the same day will be used. If both central and local assessments of the same ECG or lab test are available on the same day, the central result will take precedence over the local result.

For the overlapping visit windows at Week 12 and Week 8/16, a hierarchical algorithm will be applied as follows: always map to the Week 12 study visit if the study day falls within the visit window of the Week 12 study visit, then assess the other records for the Week 8 or Week 16 study visit. The same algorithm will be used for Week 48 and Week 52, with Week 52 taking priority.

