10. DISPOSITION AND PROTOCOL DEVIATIONS

All subjects who provide informed consent will be accounted for in this study. Inclusion criteria not met and exclusion criteria met will be listed.

Among the randomized subjects, the number and percent of subjects who completed/discontinued treatment, reasons off treatment, the number and percent of subjects who completed/discontinued the study, and reasons off study will be summarized. This summary will also be provided by region and country. The number and percent of subjects in each analysis set will be summarized for all randomized subjects. An additional summary of the number of subjects screened, the number of screen-failed subjects, and reason for screen failure will be presented for all screened subjects. A listing of subjects whose blind was broken will be provided. The number of subjects whose visit was impacted by the COVID-19 pandemic per CRF will also be summarized by nominal visit.

During site monitoring, protocol deviations will be graded as Critical, Major, or Minor.

According to ICH E3 and ICH E3(R1), important protocol deviations are a subset of protocol deviations that might significantly affect the completeness, accuracy, and/or reliability of the study data or that might significantly affect a subject's rights, safety, or well-being (ICH 1995, ICH 2012). For example, important protocol deviations might include enrolling subjects in violation of key eligibility criteria designed to ensure a specific subject population or failing to collect data necessary to interpret primary endpoints, as this may compromise the scientific value of the study.

During the review of all reported deviations, important deviations related to study inclusion or exclusion criteria, conduct of the study, patient management, or patient assessment will be identified. Where relevant the importance of a potentially important protocol deviations will be assessed in the context of the study's estimands to evaluate potential impact.

All important protocol deviations will be summarized for the FAS in the following categories in descending frequency in the etrasimod group.

All protocol deviations will be listed, including whether a deviation was impacted by the COVID-19 pandemic (Yes or No). Protocol deviation categories include but are not limited to the following:

- Informed Consent
- Eligibility and Entry Criteria
- Concomitant Medication
- Laboratory Assessment
- Study Procedures
- Serious Adverse Event

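### Protocol Table 7 still gives the Week 12/early termination visit ±3 days where Section 9.4.2 allows ±7; separately, SAP Table 2 labels labs, vital signs and biomarkers from a permitted Week 52 visit on Day 351 as Week 48

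*Protocol*

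**What the plan says.** **Week 12 and ET.** Protocol Section 9.4.2 sets ±3 days as the default from Week 2 and then widens it: "For the Week 12 through Week 48 Visits, and ET Visit, a study visit window of" ±7 days applies, with ±14 days for Week 52. In Appendix 1, both header rows of Table 7 label the column "W12/D85 / Early Termination" and give ±3 days. Footnote a to the same table says: "Subjects discontinuing prior to Week 12/Day 85 should have an Early Termination (ET) visit within 7 days of the last study treatment administration". The corresponding Table 8 column is headed "W52/D365 ± 14 Days / Early Termination", with ±7 days for the ET part. SAP Table 2 labels its row "Week 12 (Day 85 ± 7", although SAP Section 6.4 names protocol Appendix 1 as the source of the scheduled windows.

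**Week 48 and Week 52.** SAP Table 2 has two panels. The first covers safety labs, vital signs, efficacy-related biomarkers and efficacy data outside endoscopy, MMS and histology. It gives Week 48 Days 310–351 and Week 52 every day above 351. The second covers endoscopy, MMS, histology, composite endpoints and several other assessments, and gives Week 52 Days 337–393. When several results fall in one analysis visit, Section 6.4 says "the result with the date closest to the protocol scheduled day will be used in the analysis".

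**The concern.** A site or monitor working from Table 7 could log a Week 12 visit that Section 9.4.2 allows as a visit-schedule deviation, or reschedule it needlessly. The SAP lists every deviation: "All protocol deviations will be listed, including whether a deviation was impacted by the COVID-19 pandemic (Yes or No"). Protocol Section 9.1 stresses adherence to the schedule in Table 7 and allows no waivers, so nothing tells the reader that Section 9.4.2 prevails.

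The SAP cut-off is a different kind of error, because a result collected on time for Week 52 carries the wrong visit label. If the subject also has a Week 48 result for that variable, the Day 351 value loses to it and leaves the by-visit summaries and the repeated-measures model. If there is no Week 48 result, the value is reported under Week 48. In both cases Week 52 is empty for that subject unless a later record exists. Fecal calprotectin is the clearest case: Table 8 plans samples only at Weeks 24 and 52, so a Day 351 sample leaves the Week 52 analysis and lands on a visit where none was planned.

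**Working it through.** **Week 12**

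- Section 9.4.2: 85 ± 7 = Days 78–92, which is 15 days.
- Table 7 header: 85 ± 3 = Days 82–88, which is 7 days.
- Allowed by the text but outside the header: Days 78–81 and 89–92, so 15 − 7 = 8 days.
- SAP Week 12 analysis windows: Days 72–99 (first panel) and 66–113 (second panel). Since 72 ≤ 78 and 92 ≤ 99, and 66 ≤ 78 and 92 ≤ 113, every permitted day maps to Week 12 in both panels. The Per Protocol endoscopy criterion in SAP Section 5.4 also uses the analysis window, so no Week 12 data are lost.

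The sources do not all cover the same visits. Section 9.4.2 covers Week 12 and ET, SAP Table 2 covers Week 12 only, and the ±7 in Table 8 covers ET only. The Amendment 4.0 change list has an entry "Revised column header as follows" for Table 8 and none for the Table 7 header, which suggests an incomplete edit. The contradiction itself rests on the current text.

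**Week 52**

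- Permitted Week 52 days: 365 − 14 = 351 to 365 + 14 = 379, which is 29 days.
- Permitted Week 48 days: 337 ± 7 = 330–344. Day 351 is never a permitted Week 48 day.
- First-panel label for Day 351: Week 48, because that window runs to 351 and Week 52 starts at 352.
- Share of permitted Week 52 days affected: 1/29 = 3.4%.
- Closest-date rule: |351 − 337| = 14, while a permitted Week 48 result is at most 7 days from Day 337. The Week 48 result always wins.

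**All first-panel visits.** Weeks 2, 4 and 8 allow 7 days each, Weeks 12 to 48 (seven visits) allow 15 each, and Week 52 allows 29: 3 × 7 + 7 × 15 + 29 = 155 permitted days. Mapping each day through the panel leaves one in the wrong visit, Day 351.

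**Why only here.** Each cut-off from Week 2/Week 4 onward is the midpoint of adjacent scheduled days, with the tie given to the earlier visit. For example, (281 + 337)/2 = 309 and (337 + 365)/2 = 351. Elsewhere the permitted days stop at least 3 days inside the analysis window; the tightest case is Week 4, where permitted days start at 26 and the window at 23. The Week 52 allowance of 14 days equals half the 28-day gap from Week 48, so it reaches the midpoint exactly.

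**Second panel.** All of Days 351–379 lie inside 337–393, so the endpoints analysed there keep their Week 52 label.

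**The case against.** The strongest reply is that the SAP already has a rescue. Section 6.4 says Week 52 takes priority over Week 48, and footnote d to Table 2 ends by sending scheduled Week 48 and Week 52 visits found in one window to separate visits. Read generally, that sentence would place Day 351 in Week 52 for a subject with both visits. One could also take the priority rule to mean the protocol window, Day 365 ± 14, which contains Day 351.

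The literal text does not support either reading for labs, vital signs and biomarkers. The priority rule is written for overlapping windows and requires the day to lie inside the priority visit's window. The two first-panel windows do not overlap, and Day 351 is outside the Week 52 one. The protocol windows (330–344 and 351–379) do not overlap either. Footnote d is worded for rectal bleeding and stool frequency, and it is attached only to the second-panel Week 52 row.

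It is also fair to say that the midpoint convention is applied uniformly. That explains how the limit arose, but it does not make the label right.

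Several points on the other side stand:

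- The loss under the closest-date rule requires a Week 48 result for the same variable.
- The 3.4% assumes even use of the window; visits clustering near Day 365 would make it smaller.
- Footnote a to Table 7 sets a deadline after the last dose, which is not the same as a tolerance around a scheduled day. The plain contradiction is between the header and Section 9.4.2.
- The change list does not record minor editorial revisions, so a missing entry is only suggestive.
- Listed deviations are graded and only important ones are summarised, so the practical effect of the Table 7 header may be no more than listing entries.

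**Conclusion.** Both points hold, and both are minor. The Table 7 header contradicts Section 9.4.2 on 8 of 15 permitted Week 12 days and on the ET window; it affects scheduling and deviation logging, not endpoint mapping. SAP Table 2 assigns one permitted Week 52 day, Day 351, to Week 48 for the first-panel variables: 1 of 29 Week 52 days and 1 of 155 permitted days overall. The effect is confined to Week 52 by-visit summaries and the biomarker model; listings and worst-case summaries still use the values. Clinical remission, the other endoscopy-based endpoints and Week 52 symptomatic remission use Days 337–393 and are untouched. The number of subjects affected cannot be stated, because the documents give no distribution of visit days. The second point assumes that the priority rule and footnote d are applied as written.

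**What to change.** Change the Week 12/ET header in both header rows of protocol Table 7 to ±7 days. In the first panel of SAP Table 2, set Week 48 to Days 310–350 and Week 52 to Day 351 onward. All 29 permitted Week 52 days then map to Week 52, and all permitted Week 48 days (330–344) still map to Week 48. The cost is one table header and two window limits, with no new data and no change to any primary or key secondary analysis.
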